1. ABBREVIATIONS

Abbreviation/term	Definition
Adj	Adjusted
BMI	Body mass index
ECG	Electrocardiogram
ET	Early Termination population
ETEC	Enterotoxigenic Escherichia coli
FAS	Full Analysis Set population
ITT	Intention to Treat population
ICH	International Conference on Harmonisation
HDL	Low High-density Lipoprotein
HFF	Hepatic fat fraction
HOMA-IR	Homeostatic Model Assessment of Insulin Resistance
LPS	Lipopolysaccharides
Max	Maximum
MedDRA	Medical Dictionary for Regulatory Affairs
Min	Minimum
MRI	Magnetic resonance imaging
n	Number of observations
NAFL	Non-alcoholic fatty liver
NAFLD	Non-alcoholic fatty liver disease
NASH	Non-alcoholic steatohepatitis
PP	Per protocol population
Prob	Probability
SD	Standard deviation
SOC	System Organ Class
WHO DD	World Health Organisation Drug Dictionary

2. INTRODUCTION, STUDY DESIGN AND OBJECTIVES

2.1 Introduction

Non-alcoholic fatty liver disease (NAFLD) is the most common cause of chronic liver disease in most of the Western world. Approximately 7.9% of the population in the United States has persistently elevated liver enzymes without any clear aetiology and it is hypothesized that over 80% of these cases are due to NAFLD. In those who have concomitant features of metabolic syndrome, the likelihood of NAFLD exceeds 90%. Based on Magnetic Resonance Imaging (MRI), it has been estimated that the overall prevalence of NAFLD in the United States is approximately 30%.

NAFLD is the hepatic manifestation of the metabolic syndrome, a condition characterized by the presence of at least three of five co-morbidities: abdominal (central) obesity, elevated blood pressure, elevated fasting plasma glucose, high serum triglycerides and low high-density lipoprotein (HDL) levels.

The probability of having NAFLD rises with increasing body mass index (BMI) with over 80% of subjects with a BMI > 35 having NAFLD. The histological spectrum of NAFLD includes: isolated hepatic steatosis, characterized by a fatty liver with no other histological abnormalities and also referred to as non-alcoholic fatty liver (NAFL); and steatohepatitis, characterized by steatosis associated with histological abnormalities that include cytological ballooning, Mallory's hyaline, inflammation and pericellular fibrosis. NASH is defined by the presence of predominantly macrovesicular hepatic steatosis or steatohepatitis in individuals who either do not consume alcohol or consume it in quantities that are not generally considered to be harmful to the liver. There are currently no non-invasive ways to distinguish NAFLD from NASH.

IMM-124E is hyperimmune bovine colostrum that is lactose- and fat-reduced. IMM-124E is harvested from the colostrum of dairy cows which have been immunized against the outer antigens, mostly lipopolysaccharides (LPS), of the most common strains of Enterotoxigenic *Escherichia coli* (ETEC). This inoculation activates a generalized immune response in the host animal to produce antibody clones which recognize and bind with the bacterial cell-surface epitopes presented. These polyclonal antibodies can also cross-react with other similar bacterial cell surface antigens.

IMM-124E has strong binding and neutralising activity against a wide range of LPS antigens. It is hypothesised that IMM-124E anti-LPS activity decreases the challenge of LPS to the liver and down-regulates the key T regulatory cell population associated with chronic inflammation and other metabolic defects associated with NASH.

In addition to its potential effect on bacterial translocation, IMM-124E contains adjuvants which promote regulatory T cells that suppress inflammation in target organs. The dual function of this product may be synergistic in alleviating NASH.

A clear unmet medical need remains in the treatment of NASH and an oral, well tolerated treatment for this condition is needed. Bovine colostrum, either as standard or hyperimmune colostrum, has an excellent safety profile

2.2 Study design

This was to be a randomized, double blind, placebo controlled, 3-arm parallel group, multi-dose, multi-centre study. The three treatment arms include 600mg IMM-124E three times daily, 1200mg IMM-124E three times daily and matching placebo. A total of 120 subjects, randomised to the three treatment groups in 1:1:1 ratio, having been previously diagnosed with NASH will be studied during a 24 week treatment period.

An interim analysis will be planned for this study, the purpose of which will be to determine whether any safety concerns exist as well as identify any preliminary signals for efficacy through examination of the primary, secondary and exploratory endpoints. The interim analysis will occur when 80 subjects have completed the 24 weeks treatment period and have both Baseline and 24 weeks' evaluable MRI hepatic fat fraction values. Each IMM-124E dose group will be compared to the placebo treatment group using pairwise contrasts. This analysis will occur for each of the hepatic fat fraction strata because of a differential response pattern across strata that have been noticed in previous studies on NASH (Le et al., 2012; Loomba et al., 2015).

2.3 Study objectives

The primary objectives of this study are to:

- Evaluate the safety and preliminary efficacy of two dose levels of IMM-124E in reducing liver fat compared with placebo in subjects with biopsy proven NASH.

The secondary objectives are to:

- Determine the pharmacokinetic profile of IMM-124E.
- Assess the impact of treatment with IMM-124E on markers of glucose metabolism and serum lipid profile.
- Assess the impact of treatment on liver function over 24 weeks.
- Establish the recommended dose.

Exploratory objectives are to investigate the impact of treatment on potentially relevant immune and metabolic biomarkers associated with NASH.

3. ANALYSIS POPULATIONS AND GENERAL STATISTICAL METHODOLOGY

This analysis plan is based on version 1.3 of the protocol, dated 8 May 2016, and includes other changes discussed at a later date.

3.1 Analysis populations

The Safety population will consist of all subjects who received at least one dose of study drug. All safety analyses will be analysed based on the treatment actually received. A subset of the safety population will be the Early Termination (ET) population. The ET population will consist of all subjects who withdrew after being randomised but before completing the Week 24 visit.

The Intention-to-Treat (ITT) population will consist of all subjects who were randomised, regardless of whether they received study drug or not. This population will be tested only if at least one subject was randomised but did not receive any study drug. All efficacy analyses will be based on the treatment to which each subject was randomised.

Full Analysis Set (FAS) for efficacy includes all subjects who received at least one dose of study medication. Only subjects with clear documentation that no study medication was received may be excluded. In the event of treatment allocation errors, subjects will be analysed for efficacy according to the treatment to which they were randomised. The FAS population will consist of the same set of patients as the Safety population. The only difference between the Safety and FAS populations will be the treatment group patients are analysed in, if any misallocation of treatment occurs.

The per protocol (PP) population will consist of all subjects who were randomised, completed the entire 24 week treatment period, were at least 85% - 115% compliant with the study drug, had liver MRIs at baseline and Week 24 and had no major protocol violations. Major protocol violations are deviations decided and documented prior to data lock and un-blinding of the randomisation code presumed by the medical monitor of having significant potential to distort the results of the study such as where a patient has been given an incorrect dispense or where they failed to satisfy inclusion or exclusion criteria. The PP population will be analysed according to the group to which they were randomised.

3.2 Visit windows

For visits during the first four weeks of treatment, and visit window of ± 1 day will apply, whereas after four weeks of treatment and during the follow-up period, the visit window will be ± 3 days.

3.3 General statistical methodology

Treatment groups will be described as '600 mg IMM-124E', '1200 mg IMM-124E' and 'Placebo'. All tables, figures and listings will be produced for these three treatment groups. In addition, where specified, tables will be produced where subjects are grouped by baseline hepatic fat fraction, baseline HbA1c, and with a binary classification (not treated vs. treated).

General descriptive statistics for continuous measures will include number of observations (n), mean, standard deviation (SD), median, quartiles, minimum and maximum. For categorical variables, descriptive statistics will include n and percentage occurrence within the treatment group. The denominator for calculating percentage will be the number of valid observations within the treatment group.

For the basic and interim analysis, missing data will remain missing and not be imputed. However, for sensitivity measures in the final study analysis, missing values will also be imputed using a multiple imputation technique (Berglund, 2010 and Yuan, 2011).

This is a multicentre study, but no analysis using centre as a stratification factor will be performed, except for the primary endpoint, in which case the analysis will be performed on the imputed data both with and without centre as a stratification factor as a sensitivity analysis on the primary endpoint. Analysis of centre as a stratification factor will also be performed on ALT, AST, Glucose, A_{1c}, lipid profile parameters and CK-18.

Concomitant medications will be coded using the most recently available version of the World Health Organisation Drug Dictionary (WHO DD) at the time of data lock. Medications will be summarised and tabulated using the first and second levels of the dictionary. Medical history and adverse events will be coded using the most recently available version of the Medical Dictionary for Regulatory Affairs (MedDRA) at the time of data lock. Both medical history and adverse events will be summarised and tabulated using System Organ Class and Preferred Terms.

Patients given the wrong treatment will be analysed as randomised for efficacy measures (for the ITT, PP and FAS populations) and as treated for safety measures (Safety population and ET subgroup).

For safety data, if there are unscheduled visits where data values exist and those data are missing for the prior, scheduled, visit, then the values from the unscheduled visit will be imputed.

In the case of multiple occurrences of the same visit, the data from the latest visit date will be used if prior to the first dose. After the first dose, the data from the earliest visit date will be used. All data collected will be presented in the data listings.

All programming for statistical analysis, data listing and production of figures will be done in version 9.4 of SAS.

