#### 3.5.1.2 Safety Dose Modeling

IMM-124E is well tolerated in clinical studies and in the market place. While the typical dose for traveler's diarrhea is 600mg/day, doses as high as 10g four times daily have been studied. Adverse reactions have been few in number and mild in severity. In most clinical studies of bovine colostrum, there have been no treatment related adverse events reported and no clear pattern in events [Tacket *et al.*, 1992; Shield *et al.*, 1993; Mitra *et al.*, 1995; Sarker *et al.*, 1998; Huppertz *et al.*, 1999; Opekun *et al.*, 1999].

Adverse events observed include:

- nausea, flatulence [Rump *et al.*, 1992; Plettenberg *et al.*, 1993]
- nausea and vomiting in 1/24 patients [Greenberg and Cello 1996]
- mild diarrhea in 1/8 adult volunteers [Lissner *et al.*, 1998]

Tacket *et al.* (1988) reported no adverse clinical signs, but transient moderate elevations in serum levels of hepatic transaminases in volunteers who received bovine immunoglobulin concentrates prepared against *E. coli* (5/10) and rotavirus (2/10). This effect was attributed to diets high in protein provided at the hospital. Colostrum administration should be avoided in person allergic to cow's milk or with lactose intolerance.

The known safety profile of bovine colostrum gives a substantial therapeutic index. Therefore, the highest dose to be evaluated will be 3600mg/day.

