8.4 Vital signs

Vital signs, including resting pulse, systolic and diastolic blood pressures, respiratory rate, and body temperature will be summarised with change from Baseline and tabulated by visit and treatment group.

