8.5 Laboratory safety measurements

Serum biochemistry parameters will be summarised with change from Baseline and the count of clinically significant values and tabulated by visit. If multiple units are reported in the eCRF, values will be transformed to SI units prior to summary. Additionally, a serum biochemistry shift table, showing the number of normal values, abnormal (both above and below normal range) but not clinically significant, clinically significant (both above and below normal range) at Baseline and each visit during the treatment and follow-up periods will also be produced. Parameters summarised and tabulated in lipid panel, biomarkers and regulatory T cell tables will be excluded.

Haematology parameters will be summarised with change from Baseline and the count of clinically significant values and tabulated by visit. Additionally, a haematology shift table, showing the number of normal values, abnormal (both above and below normal range) but not clinically significant clinically significant (both above and below normal range) at Baseline and each visit during the treatment and follow-up periods will also be produced.

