	Shift table of serum biochemistry by visit (Safety population)
	Haematology by visit (Safety population)
	Shift table of haematology by visit (Safety population)
	Vital signs by visit (Safety population)
	Physical examination results by visit

Figure Section	Figure Title (Population)
Section 11.4	
Difference in hepatic fat between Placebo and each dose level of IMM-124E (ITT, PP, FAS populations)
 
Difference in hepatic fat between Placebo and each dose level of IMM-124E by hepatic fat category and HbA1c (ITT, PP, FAS populations) (lattice graph)
 
Difference in hepatic fat between Placebo and each dose level of IMM-124E (ITT, PP, FAS populations with MI imputation where appropriate)
 
Difference in hepatic fat between Placebo and each dose level of IMM-124E by hepatic fat category and HbA1c (ITT, PP, FAS populations with MI imputation where appropriate) (lattice graph)
 
Proportion of subjects with normal ALT by visit (ITT, PP, FAS populations)
 
MELD score by visit (ITT, PP, FAS populations)
 
Proportion of subjects with 5% reduction of hepatic fat from baseline (ITT, PP, FAS populations)
 
Proportion of subjects with 10% reduction of hepatic fat from baseline (ITT, PP, FAS populations)
 
Body mass index, waist circumference and waist:hip ratio by visit (ITT, PP, FAS populations)
 
HbA1c by visit (ITT, PP, FAS populations)
 
HOMA-IR by visit (ITT, PP, FAS populations)
 
AUDIT results by visit (ITT, PP, FAS populations)

Section 12.2	Odds ratios of most common Preferred Terms (Safety population)

Sample Tables

Primary analysis

										Group comparisons					
Treatment	Visit / Value	n	Mean	SD	Median	Quartiles 1 & 3	Min	Max	Prob = 0	Normality Prob	Change	Ranks Prob	Ranks	Permut ations	Disp- arity
Treatment 1	Screening														
	Baseline														
	Timepoint 1														
	Change to Timepoint 1														
	Adj change to Timepoint 1 Difference from Treatment 2														
	Difference from Treatment 3														
	Change to Timepoint 2...														

Primary analysis with Subgrouping

Subgroup (e.g. HFF, A1c, ALT, Fibrosis, Inflammation, ballooning)	Treatment	Visit / Value	n	Mean	SD	Median	Quartiles 1 & 3	Min	Max	Prob = 0	Group comparisons					Disparity	
											Normality Prob	Change	Ranks Prob	Ranks	Permutations		
Group 1	Treatment 1	Screening															
		Baseline															
		Timepoint 1															
		Change to Timepoint 1															

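### When the scheduled value is present, the SAP gives unscheduled safety results no place in its by-visit tables, and it plans no worst post-baseline or toxicity-grade summary

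*SAP*

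**What the plan says.** SAP 3.3 has two rules that decide which safety values are summarised. For unscheduled visits, "if there are unscheduled visits where data values exist and those data are missing for the prior, scheduled, visit, then the values" obtained there fill the gap. The section does not say what happens when there is no gap. For a visit recorded more than once, "After the first dose, the data from the earliest visit date will be used". It also promises that "All data collected will be presented in the data listings".

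The tables fed by these values are arranged by visit. In SAP 8.5, "Serum biochemistry parameters will be summarised with change from Baseline and the count of clinically significant values and tabulated by visit", and haematology is treated the same way. Shift tables for those two panels, "at Baseline and each visit during the treatment and follow-up periods will also be produced". In SAP 8.4, vital signs "will be summarised with change from Baseline and tabulated by visit and treatment group", with no shift table. The table list in SAP section 12 agrees: it has no worst post-baseline table, no table by toxicity grade and no coagulation table.

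On the protocol side, section 4.2 puts changes in vital signs and laboratory parameters in the primary safety endpoint. Section 7.2.8 collects vital signs, hematology, coagulation and chemistry at unscheduled visits where possible. Sections 12.6.2 and 12.6.3 plan laboratory and vital-sign summaries by toxicity grade.

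**The concern.** Protocol 7.2 allows extra visits when clinically indicated, so results from them are more likely than routine ones to be abnormal. The SAP tables are organised in a way that can leave those results out. Listings retain them, but a listing gives no rate by arm, and comparing arms is what a primary safety endpoint in a dose-finding trial needs.

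Transient changes are the ones most exposed, because from Week 4 scheduled chemistry is four-weekly. Protocol 3.5.1.2 mentions such a finding in an earlier challenge study: "transient moderate elevations in serum levels of hepatic transaminases in volunteers who received bovine immunoglobulin concentrates prepared against" *E. coli* (5 of 10) and rotavirus (2 of 10). The protocol says this was attributed to high-protein hospital diets, so it is not evidence of a drug effect. It does illustrate the kind of short-lived laboratory change that the tables should be able to show.

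**Working it through.** The plan states no figure to reproduce. The check is to follow a value through the rules.

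| Situation | Rule that applies | Where the value appears |
|---|---|---|
| Unscheduled value, preceding scheduled value missing | SAP 3.3 fill-in rule | By-visit summary of the earlier visit; also the shift table for biochemistry or haematology; listings |
| Unscheduled value, preceding scheduled value present | None stated | Listings; no table is assigned |
| Later repeat of the same visit after the first dose | SAP 3.3 earliest-record rule | Listings only; the first record is tabulated |

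**Effect on counts.** The tabulated results are a subset of all results after the first dose. The number of patients with at least one abnormal tabulated result is therefore at most the number with at least one abnormal result overall. Compared with using everything, each arm's count can be too low and cannot be too high. How this affects the difference between arms is unknown.

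**The adverse-event route.** Protocol 10.5 keeps asymptomatic laboratory abnormalities out of adverse-event reporting unless they are clinically significant. Its stated reason is that all laboratory data are analysed statistically against reference ranges. SAP 8.2 tabulates adverse events by arm. Putting these together:

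- A clinically significant unscheduled result can reach a by-arm table, as an adverse event.
- An asymptomatic one not judged clinically significant can miss both the adverse-event and the laboratory tables. The premise of protocol 10.5 is then not met.

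**Toxicity grades.** Protocol 12.6.2 and 12.6.3 require summaries by grade, and Appendix A supplies scales for vital signs and serum chemistry. SAP 8.4, SAP 8.5 and the table list contain no such summary, so nothing there makes up for the missing worst-value table.

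**The fill-in rule.** It has no time limit, while SAP 3.2 allows ±3 days after Week 4. Take Week 8 as Day 56 and Week 12 as Day 84. The Week 12 window opens on Day 84 − 3 = 81. A result on Day 80 could therefore be entered as Week 8, although it is 80 − 56 = 24 days late against a 3-day allowance.

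**The case against.** The strongest reply is that the SAP excludes nothing in words. SAP 3.3 covers one case and is silent on the other, and the shift tables in SAP 8.5 refer to each visit, not each scheduled visit. A reader might infer that unscheduled results never reach a table. The documents do not support that: the fill-in rule admits some, and the rest of the inference is from silence. This part of the reply stands. It does not remove the gap, because an added row for unscheduled visits would still give no per-patient worst value. If such visits shared one label, the earliest-record rule could keep only the first.

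Clinically significant results have the adverse-event route, with numbers and percentages by arm. That also stands. What is exposed is the abnormal result not judged clinically significant, and the completeness of the laboratory tables themselves.

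Keeping the earliest duplicate can preserve an initial abnormal value when the repeat is normal. This is true when choosing between first and last. It does not answer the comparison with using both.

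Two further inferences should be resisted. One is that filled-in values would be non-fasting because protocol 7.2.8 does not mention fasting. Table 1 marks clinical chemistry at unscheduled visits, and its footnote 1 requires fasting except at Screening and Week 28. The other is that the share of missed events can be computed from the 28-day spacing. That needs an assumed duration of abnormality, which the documents do not give, and it ignores the denser Day 7 and Day 14 draws.

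Finally, by-visit tables, adverse-event tables and full listings might be thought enough for an exploratory Phase 2 trial. The protocol itself asks for more, namely summaries by grade, and makes safety a primary objective.

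**Conclusion.** The point holds as a gap in the analysis rules. When the preceding scheduled value is present, the SAP assigns an unscheduled safety value to no by-visit laboratory, vital-sign or shift table. Later repeats of the same visit after the first dose are left out of the summaries. No worst post-baseline or toxicity-grade summary is planned to catch either. Abnormal results between visits may appear only in listings if not judged clinically significant, and only as adverse events if they are.

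By-arm counts of abnormal values can be too low. The size cannot be given, since neither document states how often unscheduled visits or repeats are expected. The conclusion assumes that the SAP's silence is applied literally and that by-visit tables are built from the visits it names. The primary efficacy analysis is not affected.

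**What to change.** Before the randomisation code is broken:

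- **SAP 3.3.** State that by-visit means use scheduled values, and that all unscheduled and repeat results after the first dose enter the worst-value tables below.
- **SAP 3.3, fill-in rule.** Either do not carry an unscheduled value back to a missed scheduled visit, or do so only if it falls within the SAP 3.2 window for that visit.
- **SAP 8.4, 8.5 and the table list.** Add, by arm, a baseline-to-worst-post-baseline shift or toxicity-grade table for chemistry, haematology, coagulation and vital signs, using every result after the first dose. For chemistry and vital signs, Appendix A grades would also meet protocol 12.6.2 and 12.6.3. Appendix A shows no haematology or coagulation grades, so for those panels the normal/abnormal/clinically significant categories already in SAP 8.5 can be used.

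The cost is some SAP wording and a few extra tables. No new data are needed, because the results are already collected. The downside for the sponsor is that abnormal counts will be slightly higher.

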### 7.2 Study Procedures and Assessment Periods

The study procedures to be conducted for each subject enrolled in the study are listed below. Additional information on the study procedures is provided in [Section 7.4](#). Any deviation from protocol procedures must be noted in the source notes and the Sponsor notified.

Additional visits and/or assessments may be conducted as clinically indicated. For these additional assessments, data may be collected on unscheduled Case Report Form (CRF) pages provided, together with all adverse events (AEs) and concurrent medication that must be recorded throughout the study period.

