### 7.3.6 Safety Laboratory Assessments

Blood will be collected at Screening, Baseline, and scheduled clinic visits (except D3) and at the Withdrawal visit if applicable. These should be collected within the visit window period required for the visit date (see [Section 7.4](#)). Urine will be collected at Screening only.

Clinical chemistry will be performed at the Baseline visit and scheduled clinic visits (except D3) with the subject having fasted for at least 8 hours before sample collection. HOMA-IR score will be calculated when fasting glucose and insulin measurements have been reported, according to the HOMA-IR algorithm (Appendix C).

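### SAP 3.3 fills a missing scheduled safety value from a following unscheduled visit with no time window, no pre-dose condition for Baseline and no on-treatment condition

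*SAP*

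**What the plan says.** SAP 3.3 has a general statement and a safety rule. The general statement is "For the basic and interim analysis, missing data will remain missing and not be imputed". The safety rule, later in the same section, covers unscheduled visits that have data: if "those data are missing for the prior, scheduled, visit, then the values from the unscheduled visit will be imputed". The rule states no maximum interval, no condition relative to dosing and no exemption for any visit.

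SAP 3.2 sets a window of ±1 day in the first four weeks; "after four weeks of treatment and during the follow-up period, the visit window will be ± 3 days". Nothing links these windows to the filling rule.

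SAP 3.3 separates pre-dose from post-dose data in one place only. When the same visit occurs more than once, the latest date is used before the first dose and the earliest date after it.

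Protocol 7.2 says of unscheduled contacts: "Additional visits and/or assessments may be conducted as clinically indicated". Protocol 7.2.8 lists what they collect where possible, including vital signs, hematology, coagulation and clinical chemistry. SAP 8.4 summarises vital signs as change from Baseline by visit. SAP 8.5 does the same for biochemistry and haematology, and adds shift tables of categories "at Baseline and each visit during the treatment and follow-up periods will also be produced".

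**The concern.** Changes in vital signs and laboratory parameters are part of the primary safety endpoint (Protocol 4.2). The by-visit tables are useful only if a value labelled Baseline was taken before drug, and a value labelled with a treatment visit was taken near that visit and on drug. The filling rule guarantees neither.

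Baseline matters most because one value enters many comparisons. Protocol Table 1 schedules vital signs, chemistry and hematology at nine visits after Baseline (Day 7, Day 14, Weeks 4, 8, 12, 16, 20, 24 and 28). A post-dose value in the Baseline slot shifts the reported change at all nine for that subject and parameter, and can change the starting category in the shift table.

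**Working it through.** The plan gives no figure on this point, so there is none to reproduce. The check has three parts.

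**1. Can a post-dose value become Baseline?** Under Protocol 7.2.3, randomization and the start of dosing both take place at the Baseline visit (Day 0), with the first dose in the clinic where possible. An unscheduled sample taken before that visit has Screening as its prior scheduled visit, so the rule would not use it for Baseline. Only a sample taken after the Baseline visit qualifies, and that is normally post-dose. The repeat-visit rule does not prevent this, because an unscheduled visit is not a second occurrence of Baseline.

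Write the true pre-dose value as y0, the substituted value as y0 + d, and the value at visit t as yt. The reported change is yt − (y0 + d) = (yt − y0) − d. The error −d is the same at every later visit.

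**2. Can an off-drug value become Week 24?** Unused medication is returned at Week 24 (Protocol 7.2.9) and follow-up comes four weeks after treatment ends (Protocol 7.2.10). An unscheduled visit between the two has Week 24 as its prior scheduled visit. If a Week 24 safety value is missing, the rule fills it with one taken off drug.

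**3. How far can a value be moved?** Assume that the prior visit is the scheduled visit immediately before, and that the next scheduled visit is attended. Nominal days and windows are from Protocol Table 1 and SAP 3.2.

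- Latest unscheduled day = nominal day of next visit + its window − 1
- Offset = latest day − nominal day of the filled visit
- Excess = offset − window of the filled visit

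| Filled visit | Nominal day, window | Latest unscheduled day | Offset (days) | Excess (days) |
|---|---|---|---|---|
| Baseline | 0, none | 7 + 1 − 1 = 7 | 7 | 7 |
| Day 7 | 7, ±1 | 14 + 1 − 1 = 14 | 7 | 6 |
| Day 14 | 14, ±1 | 28 + 1 − 1 = 28 | 14 | 13 |
| Week 4 | 28, ±1 | 56 + 3 − 1 = 58 | 30 | 29 |
| Week 8 | 56, ±3 | 84 + 3 − 1 = 86 | 30 | 27 |
| Week 24 | 168, ±3 | 196 + 3 − 1 = 198 | 30 | 27 |

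Weeks 12, 16 and 20 give the same result as Week 8. If the Day 3 contact counts as a scheduled visit, the Baseline limit falls to 3 + 1 − 1 = Day 3, which is still post-dose. On nominal dates alone, ignoring the next visit's +3 days, the Week 8 offset is 84 − 1 − 56 = 27 days and the excess is 24. All of these are upper limits, not expected shifts.

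**The case against.** The strongest defence has four parts.

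- **The rule only fills gaps.** It never displaces an observed scheduled value, and showing an observed abnormality may be more cautious than a blank cell. That is fair as far as it goes. However, SAP 3.3 already puts all collected data in the listings, so leaving the cell empty hides nothing, whereas filling it assigns the value to the wrong time. For Baseline the caution argument reverses: an abnormal post-dose value placed there can make later abnormalities look like no change.
- **The Baseline case is uncommon.** It needs a missing Day 0 value and an unscheduled sample soon afterwards. This stands. The documents give no rate for either, and the damage is confined to that subject and parameter.
- **The intention is probably a pre-dose Baseline.** The repeat-visit rule suggests so. But it does not cover unscheduled visits, and a program written from the text would not apply it to them.
- **The tables are descriptive, in a trial called exploratory.** True, and this limits the consequence. They are still the tables that report part of the primary safety endpoint.

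Four stronger readings are tempting, but the documents do not support them.

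- **Non-fasting glucose enters a fasting series.** Protocol 7.3.6 asks for fasting chemistry at Baseline and "scheduled clinic visits (except D3) with the subject having fasted for at least 8 hours before sample collection", while 7.2.8 does not mention fasting. But Table 1 marks chemistry at unscheduled visits, and its footnote 1 requires fasting except at Screening and Week 28.
- **The rule creates a Day 3 laboratory value.** No laboratory tests are scheduled on Day 3, so none can be missing there.
- **An unscheduled value from any later time can fill the gap.** The reference to the prior scheduled visit implies a limit at the next one, and the table above assumes that limit.
- **Abnormal counts are inflated more in one arm.** Unscheduled visits can be prompted by events, but nothing in the documents shows a difference between arms.

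**Conclusion.** The concern holds. Nothing else in the SAP or protocol stops the rule from placing a value taken after the Baseline visit into Baseline, an off-drug value into Week 24, or a value up to about 30 days late (27 beyond the window) into Weeks 8 to 20.

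The 30-day figure assumes that the prior visit is the one immediately before and that the next visit takes place at the end of its window. The Baseline conclusion assumes that the first dose is taken at the visit, as the protocol intends where possible.

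The effect on the results cannot be sized, because the documents do not say how often scheduled values will be missing or unscheduled visits will occur. The rule covers safety data only, so the MRI endpoint is not affected. ALT, AST, GGT, bilirubin and albumin are also secondary endpoints, and the SAP does not say whether filled values enter those analyses; the conclusion does not depend on that.

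**What to change.** Amend the safety-filling sentence in SAP 3.3 before unblinding so that:

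- an unscheduled safety value fills a missing scheduled value only if it lies within that visit's SAP 3.2 window;
- Baseline is filled only by the last non-missing value before the first dose, whether from Screening or an unscheduled visit;
- a value taken after the last dose does not fill Week 24 or any other on-treatment visit.

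Other unscheduled values stay in the listings already planned, so no new table is needed.

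The cost is one short SAP revision and a date check in the program. The dates of first and last treatment are already needed for exposure under SAP 8.1, which also provides for estimating an unknown last-treatment date. The downside is a few more empty cells in the by-visit tables.
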